8.6 Safety signal detection

Selected data from this study will be reviewed periodically to detect as early as possible any safety concern(s) related to the study medication so that Investigators, clinical study participants, regulatory authorities, and IECs will be informed appropriately and as early as possible.

The Study Physician or medically qualified designee/equivalent will conduct an ongoing review of SAEs and perform ongoing SAE reconciliations in collaboration with the UCB PS representative.

As appropriate for the stage of development and accumulated experience with the study medication, medically qualified personnel at UCB may identify additional safety measures (eg, AEs, vital signs, laboratory, or ECG results) for which data will be periodically reviewed during the course of the study.

8.7 Treatment of overdose

For this study, any dose of PSL greater than that prescribed in the protocol will be considered an overdose. Overdose events are only considered AEs or SAEs if there are associated clinical signs and symptoms or if the act of taking the excess study medication itself is an AE or SAE (eg, suicide attempt).

UCB does not recommend any specific treatment for an overdose.

In the event of an overdose, the Investigator should:

1. Contact the UCB Study Physician immediately.
2. Closely monitor the participant for any AE/SAE and laboratory abnormalities until study medication can no longer be detected systemically (at least 3 days).
3. Obtain a plasma sample for PK analysis within 3 days from the date of the last dose of study medication if requested by the UCB Study Physician (determined on a case-by-case basis).
4. Document the quantity of the excess dose as well as the duration of the overdose in the eCRF.

Decisions regarding dose interruptions or modifications will be made by the Investigator in consultation with the UCB Study Physician based on the clinical evaluation of the study participant.

8.8 Genetics

Blood samples will be collected prior to the first dose of study medication on Day 1 of Treatment Period 1 and stored for possible ADME genotyping for drug metabolizing enzymes (depending on the outcome of PSL and metabolite PK analyses, if required).

8.9 Biomarkers

Biomarkers are not evaluated in this study.

8.10 Medical resource utilization and health economics

Medical resource utilization and health economics are not evaluated in this study.

9 STATISTICAL CONSIDERATIONS

A description of statistical methods follows and will be described in more detail in the Statistical Analysis Plan (SAP). Deviations in analyses from the final SAP will be documented in the clinical study report.

9.1 Definition of analysis sets

The following are the defined analysis sets:

- Enrolled Set (ES): All study participants who have signed the ICF.
- Randomized Set (RS): All enrolled study participants who are randomized will be included in the RS.
- Safety Set (SS): All enrolled study participants who receive at least 1 dose of study medication.
- Pharmacokinetic Per-Protocol Set (PK-PPS): All enrolled study participants who receive at least 1 dose of study medication and who have no important protocol deviations affecting the PK and for whom at least 1 measurable concentration is available.

For definitions of the Pharmacodynamic Per-Protocol Set (PD-PPS) and other relevant PD analysis sets, refer to the SAP.

9.2 General statistical considerations

Statistical evaluation will be performed by the Sponsor or designee and supervised by the Early Development Statistics Department of UCB. All statistical analyses will be performed using SAS® Version 9.4 or later (SAS Institute, Cary, NC, USA).

For continuous variables, summary statistics will include number of study participants, mean, median, standard deviation (SD), minimum, and maximum (geometric mean and geometric coefficient of variation [CV] for plasma concentrations and PK parameters). Categorical endpoints will be summarized using number of study participants, frequency, and percentages. Missing data will not be imputed.

If not otherwise stated, Baseline for each Treatment Period will be the last assessment prior to dosing. Measurement of specific Baseline values will be described in the SAP.

9.3 Planned efficacy/outcome analyses

As efficacy was not evaluated in this study, there will be no primary efficacy endpoint.

9.4 Planned PD analyses

9.4.1 Analysis of the primary ECG endpoint

During the hour prior to administration of the first dose of each Treatment Period, up to 10 replicate ECGs extracted from the Holter record (at -0.75, -0.5, and -0.25 hours) will serve to provide a predose time-averaged Baseline for that Treatment Period and use to compute change from Baseline QTcF (Δ QTcF).

The primary objective of evaluating the effects on QTc interval of high-dose PSL in comparison to placebo will be analyzed as follows:

- The primary analysis will be based on a by-time point analysis to evaluate the effect of PSL on the $\Delta\Delta$ QTcF at each postdose time point using the Intersection Union Test (IUT). Moxifloxacin will be used for confirmation of assay sensitivity.

Further detail on the primary endpoint analysis will be provided in the SAP.

9.4.2 Analysis of the secondary ECG endpoints

The secondary effects on cardiac repolarization (QTc interval) of high-dose PSL in comparison with placebo and moxifloxacin will be analyzed as follows:

- The effect of PSL on placebo-corrected change from Baseline in HR, PR, and QRS ($\Delta\Delta$ HR, $\Delta\Delta$ PR, and $\Delta\Delta$ QRS) will also be evaluated using the IUT.
- Assay sensitivity will also be evaluated using by-time point analysis of the effect on $\Delta\Delta$ QTcF of moxifloxacin using a similar model as for the primary analysis.
- An analysis of categorical outliers will be performed for changes in HR, QTcF, PR, QRS, T-wave morphology and U-wave presence.
- The Δt_{max} will be evaluated using an analysis of variance (ANOVA) mixed-effect model by study drug (PSL 400mg bid, and moxifloxacin 400mg), with the treatment (active treatment and placebo) as fixed effects. A 95% one-sided confidence interval (CI) (equivalent to 90% two-sided CI) of the mean difference between each active treatment and placebo will be derived from ANOVA.

Further detail on the secondary endpoint analyses will be provided in the SAP.

9.4.3 Analysis of the other PD endpoints

Results of the other PD endpoints and analyses will be reported in either the Clinical Study Report or an overarching Cardiac Safety Report.

- The relationship between plasma concentrations of PSL and its major metabolites [REDACTED] and Δ QTcF will be evaluated using a linear mixed-effects modeling approach (Garnett et al, 2018).

9.5 Planned PK analyses

The planned PK analyses will be estimated using noncompartmental analysis (NCA) with Pharsight Phoenix® WinNonlin® v6.3 (or higher) software.

The planned secondary PK endpoints of PSL include the parameters $C_{max,ss}$, t_{max} , and AUC_{τ} at steady state (Target Dose Day [Day 8]).

The planned other PK endpoints of PSL include the parameters AUC_{0-12} , C_{max} , and t_{max} (single dose), and $CL_{ss/F}$ and C_{trough} (multiple dose).

The planned other PK endpoints of the major metabolites of PSL (██████████) include the parameters AUC_{0-12} , C_{max} , t_{max} , and metabolic ratios for C_{max} and AUC_{0-12} (single dose) and AUC_{τ} , AUC_{0-t} , $CL_{ss/F}$, C_{trough} , $C_{max,ss}$, t_{max} and metabolic ratios for $C_{max,ss}$ and AUC_{τ} (multiple dose).

If required, the planned other PK endpoints of moxifloxacin include the parameters AUC , AUC_{0-t} , $t_{1/2}$, C_{max} , and t_{max} (single dose).

The individual plasma concentrations and PK parameters of PSL, ██████████ and possibly moxifloxacin will be summarized by day (Day 1 or Day 8) using descriptive statistics (number of observations, geometric mean, lower and upper 95% CI, geometric CV, arithmetic mean, SD and CV, median, and minimum and maximum value) and graphical displays.

9.6 Planned safety analyses

All safety analyses will be performed using the SS. All safety variables will be listed and summarized by each study part and treatment.

All AEs will be coded using the Medical Dictionary for Regulatory Activities (MedDRA®) and characterized as pretreatment and treatment-emergent according to the intake of the study medications. All AE data will be listed by study participant number, visit, treatment, and time. The listings will include the following data pertaining to the AEs: start and end dates with relative days to study medication administration, duration, intensity, seriousness, relationship to study medication, action taken, and final outcome.

The occurrence and incidence of TEAEs will be summarized by study part according to the intake of study medication (pretreatment or treatment-emergent) and by intensity or relationship to PSL.

Safety laboratory measurements, vital signs, and 12-lead/Holter ECG parameters will be tabulated by Treatment Period using descriptive statistics. Laboratory values outside the reference range will be flagged in the listings. Any PDILI events will be listed.

Data of assessment of suicidality (C-SSRS) will be listed.

Physical and neurological examination abnormalities will be listed.

9.7 Handling of protocol deviations

Important protocol deviations are deviations from the protocol which potentially could have a meaningful impact on study conduct or on the primary PK outcome (or primary PD outcome) for an individual study participant. Study participants will be excluded from the PK-PPS (or PD-PPS) only when there is documented evidence that they received no treatment. The criteria for identifying important protocol deviations and the classification of important protocol deviations will be defined within the relevant protocol deviation specification document, which is part of the study Data Cleaning Plan. To the extent feasible, rules for identifying protocol

deviations will be defined without review of the data and without consideration of the frequency of occurrence of such deviations. Whenever possible, criteria for identifying important protocol deviations will be implemented algorithmically to ensure consistency in the classification of important protocol deviations across all study participants.

Important protocol deviations will be reviewed as part of an ongoing blinded data cleaning process prior to database lock to confirm exclusion from analysis sets.

9.8 Handling of dropouts or missing data

The methods for handling dropouts will be described in the SAP. Data of study participants prematurely terminating the study will be used to the maximum possible extent. No procedures for replacing missing data are intended. If a Baseline value is missing or not reliable, the last value before administration of study medication will serve as Baseline.

9.9 Planned interim analysis and data monitoring

No formal interim analyses are planned.

9.10 Determination of sample size

The sample size for this study is based on the most stringent of the requirements for the test compound (PSL) and for the positive control (moxifloxacin).

A sample size of up to 54 study participants was chosen to obtain 49 evaluable study participants who will complete the study. Assuming a 1-sided 5% significance level and a within-study participant SD of 8ms for $\Delta QTcF$ for all treatment groups and a true mean difference of 3ms in $\Delta QTcF$ between PSL and placebo, based on the calculation of the sample size for a TQT study (Zhang and Machado, 2008), a sample size of 49 evaluable study participants will provide a power of 96% to demonstrate that the upper limit of all the 2-sided 90% CIs on $\Delta\Delta QTcF$ will fall below 10ms for up to 11 postdose time points.

Sample size calculation for assay sensitivity: Based on the calculation of the sample size for a TQT study (Zhang and Machado, 2008), as the test will be performed at 3 prespecified time points separately, a one-sided 5% significance level (with adjusted one-sided significance levels of 5%, 2.5%, and 1.67%) will be used in addition to a within-study participant SD of 8ms for $\Delta QTcF$ and a true effect of moxifloxacin of 10ms. A sample size of 49 evaluable study participants will provide a power of 99% to demonstrate assay sensitivity of excluding a mean difference of 5ms in $\Delta QTcF$ between moxifloxacin and placebo groups, ie, the lower limit of the 2-sided 90% CI of $\Delta\Delta QTcF$ will exceed 5msec at least one of the 3 prespecified time points.

To achieve a balanced design, and to allow for a few dropouts, it is planned to recruit up to 54 study participants.

Dropouts may be replaced at the discretion of the principal Investigator and Sponsor, depending on the circumstances.

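### Section 9.10 gives two incompatible success rules for assay sensitivity: multiplicity-adjusted levels for three time points, and an unadjusted 90% CI at any one of them

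*Protocol*

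**What the plan says.** The assay-sensitivity paragraph of Protocol section 9.10 makes two statements about the moxifloxacin test.

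- **Adjusted levels.** The reason given is multiplicity: "as the test will be performed at 3 prespecified time points separately". The overall level is "a one-sided 5% significance level", and the paragraph continues "with adjusted one-sided significance levels of 5%, 2.5%, and 1.67%) will be used". These levels are 0.05/1, 0.05/2 and 0.05/3.
- **CI criterion.** The next sentence restates success, introduced as an equivalent, as "the lower limit of the 2-sided 90% CI of" the placebo-corrected QTcF change that "will exceed 5msec at least one of the 3 prespecified time points".

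The power claim sits in the same sentence as the CI criterion: "A sample size of 49 evaluable study participants will provide a power of 99% to demonstrate assay sensitivity".

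No other part of the protocol decides between the two. Section 9.4.1 says only that moxifloxacin confirms assay sensitivity. Section 9.4.2 says "Assay sensitivity will also be evaluated using by-time point analysis of the effect on" moxifloxacin, with a model like that of the primary analysis. Neither section gives a CI level or a multiplicity procedure for this comparison.

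**The concern.** A 2-sided 90% CI with its lower limit above 5 ms is a one-sided test at 5%. Accepting it at any one of three time points is the unadjusted procedure that the preceding sentence sets aside. The two rules can therefore give opposite verdicts on the same data.

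No standard procedure built on 5%, 2.5% and 1.67% closes the gap. Under Bonferroni or Holm, the first rejection has to be made at 1.67%. Under Hochberg, the 5% level is enough only when all three time points pass, not when one does.

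The stake is the credibility of a negative padsevonil result, which depends on the study having shown that it can detect a QTc effect. If the moxifloxacin result falls near the threshold, the protocol does not say whether that check was passed. If the CI rule is applied, the stated one-sided 5% level is not kept.

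**Working it through.** **Inputs (all from section 9.10).** Within-participant SD 8 ms; 49 evaluable participants; true moxifloxacin effect 10 ms; threshold 5 ms; three time points; stated power 99%. The correlation between time points is not given, so a range is assumed below.

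**Standard error.** For a crossover difference, SE = 8 × √(2/49) = 1.616 ms. For t-based results, 48 df are used.

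**Check on the method.** The padsevonil power in the same section has a true difference of 3 ms, a limit of 10 ms and 11 time points. Per time point, Φ(7/1.616 − 1.645) = 0.9964. For 11 independent time points, 0.9964^11 = 0.961, which matches the stated 96%.

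**The stated 99% for moxifloxacin.** Noncentral t at a true 10 ms gives these powers per time point:

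| One-sided level | Per time point | At least one of 3, if independent |
|---|---|---|
| 5% (90% CI) | 92.0% | 1 − (1 − 0.920)³ = 99.95% |
| 1.67% (96.67% CI) | 81.4% | 1 − (1 − 0.814)³ = 99.4% |

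Under independence, 99% is nearer the adjusted rule. This is only suggestive: at correlation 0.5 the CI rule itself has a power of about 99%.

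**Smallest observed effect that passes at one time point.**

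- 90% CI: 5 + 1.677 × 1.616 = 7.71 ms
- 95% CI: 5 + 2.011 × 1.616 = 8.25 ms
- 96.67% CI: 5 + 2.191 × 1.616 = 8.54 ms

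A best time point between 7.71 and 8.54 ms passes the CI rule. It fails Bonferroni or Holm. Under Hochberg it fails unless all three time points exceed 7.71 ms or two exceed 8.25 ms.

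**False-positive rate when the true effect is 5 ms at all three time points.** Under independence, the CI rule gives 1 − 0.95³ = 14.3% and the 1.67% level gives 1 − (1 − 0.05/3)³ = 4.9%. Simulation of 49 paired differences at three equicorrelated time points (400,000 trials per case) gives, for the CI rule:

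| Assumed correlation | 0 | 0.25 | 0.5 | 0.7 | 0.9 | 0.95 |
|---|---|---|---|---|---|---|
| False-positive rate | 14.3% | 13.3% | 11.9% | 10.4% | 8.0% | 7.1% |

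Under the adjusted levels the rate starts at 4.9% and falls as correlation rises, to 2.5% for Bonferroni/Holm and 3.5% for Hochberg.

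With true effects of 5, 4 and 4 ms (an assumption), the CI rule gives about 7.3% at correlation 0, 6.5% at 0.5 and 5.2% at 0.9.

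**How often the rules disagree at the planned 10 ms effect.** Power under the CI rule minus power under Hochberg (normal theory):

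- correlation 0: 99.96% − 99.65% = 0.3 points
- correlation 0.5: 99.07% − 96.79% = 2.3 points
- correlation 0.9: 96.06% − 91.50% = 4.6 points

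**Secondary: power under the adjusted levels.** Section 9.4.1 uses one set of predose ECGs that "will serve to provide a predose time-averaged Baseline for that Treatment Period". All time points in a period therefore share the same baseline error, and independence is optimistic. The t-based simulation gives:

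| Assumed correlation | 0 | 0.25 | 0.5 | 0.7 | 0.9 |
|---|---|---|---|---|---|
| Bonferroni/Holm | 99.4% | 98.0% | 95.8% | 92.9% | 88.3% |
| Hochberg | 99.5% | 98.3% | 96.3% | 93.9% | 90.6% |

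Treating the variance as known raises these figures by at most about 1.4 points.

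**The case against.** The best defence is that this is a sample-size paragraph. Its operative statement attaches to the adjusted levels, and the 90% CI is loose shorthand for the nominal 5% level. Sections 9.4.1 and 9.4.2 leave analysis detail to the SAP, so not naming a multiplicity procedure there is no defect. That last point stands, and the finding does not rest on it. The shorthand reading fails on the phrase about at least one time point: with these levels, 90% CIs suffice only if all three pass. A SAP that follows either statement departs from the other.

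Three limits on size also stand. The 7–14% range needs a true moxifloxacin effect of exactly 5 ms at every time point, half the assumed 10 ms, and arises only if the CI rule governs. Under Hochberg, other time points can rescue a result in the 7.7–8.5 ms window. At the planned effect the rules seldom disagree.

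The stated 99% does not settle which rule was intended, because the CI rule gives about the same figure at correlation 0.5. It remains suggestive, because the padsevonil 96% in the same section matches an independence calculation. The contradiction does not depend on that inference.

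**Conclusion.** The concern holds. Section 9.10 prescribes two decision rules that can disagree, and nothing else in the protocol chooses between them. This is a rule stated wrongly, not a detail left for the SAP.

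The consequence is confined to moxifloxacin results near the threshold and to the error rate claimed for the test. That rate is up to 14.3% under the CI rule in the worst case with independent time points, and at most 4.9% under the adjusted levels. The figures rest on the protocol's SD and sample size, equal correlation between time points, and correlations that had to be assumed.

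The stated 99% power is sound for independent time points. It is optimistic for the adjusted rule if time points are positively correlated. Neither the sample size nor the padsevonil test is affected. The point should be fixed, and the remedy is a wording change.

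**What to change.** Replace the CI clause in section 9.10 with a single rule that names the multiplicity procedure and uses the CI level belonging to it. Two forms fit the levels already stated:

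- **Bonferroni or Holm:** lower limit of the 2-sided 96.67% CI above 5 ms at one or more of the three time points.
- **Hochberg:** lower limit above 5 ms for the 90% CI at all three time points, or the 95% CI at two, or the 96.67% CI at one.

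The choice is the sponsor's. It should be fixed before unblinding, and the SAP should use the same rule. Section 9.10 should also say that the 99% power assumes independent time points, or restate it for an assumed correlation.

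The cost is a few lines of text and possibly a slightly lower stated moxifloxacin power. No participants are added and the design does not change.

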10 SUPPORTING DOCUMENTATION AND OPERATIONAL CONSIDERATIONS

10.1 Appendix 1: Regulatory, ethical, and study oversight considerations

10.1.1 Regulatory and ethical considerations

The study will be conducted under the auspices of an IEC, as defined in local regulations, ICH-Good Clinical Practice (GCP), and in accordance with the ethical principles that have their origin in the Declaration of Helsinki.

The Investigator/UCB will ensure that an appropriately constituted IEC that complies with the requirements of the current ICH-GCP version or applicable country-specific regulations will be responsible for the initial and continuing review and approval of the clinical study. Prior to initiation of the study, the Investigator/UCB will forward copies of the protocol, ICF, IB, Investigator's curriculum vitae (if applicable), advertisement (if applicable), and all other participant-related documents to be used for the study to the IEC for its review and approval.

Before initiating a study, the Investigator will have written and dated full approval from the responsible IEC for the protocol.

The Investigator will also promptly report to the IEC all changes in the study, all unanticipated problems involving risks to participants or others, and any protocol deviations, to eliminate immediate hazards to participants.

The Investigator will not make any changes in the study or study conduct without IEC approval, except where necessary to eliminate apparent immediate hazards to the participants. For minor changes to a previously approved protocol during the period covered by the original approval, it may be possible for the Investigator to obtain an expedited review by the IEC as allowed.

As part of the IEC requirements for continuing review of approved studies, the Investigator will be responsible for submitting periodic progress reports to the IEC (based on IEC requirements), at intervals appropriate to the degree of participant risk involved, but no less than once per year. The Investigator should provide a final report to the IEC following study completion.

UCB (or its representative) will communicate safety information to the appropriate regulatory authorities and all active Investigators in accordance with applicable regulatory requirements. The appropriate IEC will also be informed by the Investigator or the Sponsor, as specified by the applicable regulatory requirements in each concerned country. Where applicable, investigators are to provide the Sponsor (or its representative) with evidence of such IEC notification.

10.1.2 Financial disclosure

Insurance coverage will be handled according to local requirements.

Finance and insurance are addressed in the Investigator and/or CRO agreements, as applicable.

10.1.3 Informed consent process

Study participant's informed consent must be obtained and documented in accordance with local regulations, ICH-GCP requirements, and the ethical principles that have their origin in the principles of the Declaration of Helsinki.

Prior to obtaining informed consent, information should be given in a language and at a level of complexity understandable to the participant in both oral and written form by the Investigator (or designee). Each study participant will have the opportunity to discuss the study and its alternatives with the Investigator.

Prior to participation in the study, the ICF should be signed and personally dated by the study participant, or his/her legal representative, and by the person who conducted the informed consent discussion (Investigator or designee). The study participant or his/her legal representative must receive a copy of the signed and dated ICF. As part of the consent process, each study participant must consent to direct access to his/her medical records for study-related monitoring, auditing, IEC review, and regulatory inspection.

If the ICF is amended during the study, the Investigator (or the Sponsor, if applicable) must follow all applicable regulatory requirements pertaining to the approval of the amended ICF by the IEC and use of the amended form.

The study participant may withdraw his/her consent to participate in the study at any time. A study participant is considered as enrolled in the study when he/she has signed the ICF. An eCRF must not be started, nor may any study specific procedure be performed for a given study participant, without having obtained his/her written consent to participate in the study.

